8.2 Background Characteristics

8.2.1 Subject Disposition

For the Treatment Period in all Parts, subject disposition will be summarized as described below.

The number of subjects in the following categories will be summarized by treatment group and overall, for Parts 1 and 3:

- All Subjects Set (randomized or dosed)
- Randomized
- Safety Set
- Randomized but not dosed in Period 1 of the Treatment Period
- Full Analysis Set (FAS)

The number of subjects in the following categories will be summarized by treatment group and overall for Part 2:

- Randomized or dosed in the Period 1 of the Treatment Period
- Randomized
- Safety Set for the Treatment Period
- Randomized but not dosed in Period 1 of the Treatment Period
- Full Analysis Set (FAS)

The number and percentage (based on FAS) of subjects in each of the following disposition categories will be summarized by treatment group and overall:

- Completed study drug treatment (separately by Periods 1 and 2 for both Part 1 and Part 2)
- Prematurely discontinued treatment and the reason for discontinuation (i.e., discontinued all study drugs) (separately by Periods 1 and 2 for both Part 1 and Part 2)
- Completed study (i.e., completed Safety Follow-up Visit or completed all study drugs and re-entered Study 661-110 without Safety Follow-up per protocol)
- Prematurely discontinued the study and the reason for discontinuation

For the Run-in Period in Part 2, a separate disposition table will be provided with the following categories:

- Safety Set for the Run-in Period
- Enrolled but not dosed in the Run-in Period
- Completed treatment in the Run-in Period (i.e., completed randomization)
- Prematurely discontinued treatment during the Run-in Period and the reason for treatment discontinuation (i.e., discontinued all study drugs in the Run-in Period)

- Prematurely discontinued the study during the Run-in Period and the reason for study discontinuation

A listing will be provided by part, for subjects who discontinued treatment (including the Run-in Period in Part 2) or who discontinued study with reasons for discontinuation. A randomization listing of subjects will also be provided, by part.

8.2.2 Demographics and Baseline Characteristics

Demographics, medical history and baseline characteristics will be summarized based on the FAS, and presented by treatment group and overall, for each part, as applicable.

Demographic data will include the following:

- Age at baseline (in years)
- Sex (female and male)
- Ethnicity (Hispanic or Latino, not Hispanic or Latino, and not collected per local regulations)
- Race (White, Black or African American, Asian, American Indian or Alaska Native, Native Hawaiian or Other Pacific Islander, and Other)

Baseline characteristics will include the following:

- Weight (kg)
- Height (cm)
- BMI (kg/m^2)

Stratification categories will include the following:

- ppFEV₁ at stratification (< 70 and ≥ 70)

For Parts 1 and 3, ppFEV₁ stratification (<70 versus ≥ 70) will be performed at Stratification Visit for subjects being treated with 1 or more CFTR modulators (investigational or approved) within 14 days of the Screening Visit. For subjects not being treated with any CFTR modulators within 14 days of the Screening Visit, the Screening Visit spirometry assessment can be used for stratification.

For subjects in Part 2, the ppFEV₁ assessment for stratification of randomization will be done at the Day -14 Visit.

Disease characteristics will include the following:

- ppFEV₁ at baseline (<40 , ≥ 40 to <70 , ≥ 70 to ≤ 90 , >90)
- ppFEV₁ at baseline (continuous)
- Sweat Chloride at baseline (continuous)
- FEV₁ (L) at baseline (continuous)
- CFQ-R Respiratory Symptoms domain at baseline (continuous)
- Prior use of dornase alfa before first dose of study drug in the Treatment Period (Yes, No)

- Prior use of inhaled antibiotic before first dose of study drug in the Treatment Period (Yes, No)
- Prior use of any bronchodilator before first dose of study drug in the Treatment Period (Yes, No)
- Prior use of any inhaled bronchodilator before first dose of study drug in the Treatment Period (Yes, No)
- Prior use of any inhaled hypertonic saline before first dose of study drug in the Treatment Period (Yes, No)
- Prior use of any inhaled corticosteroids before first dose of study drug in the Treatment Period (Yes, No)
- Infection with *Pseudomonas aeruginosa* at baseline (Positive, Negative)

A summary of medical history will be provided by MedDRA System Organ Class (SOC) and Preferred Term (PT) for the FAS. In addition, the number of subjects reported to have had positive cultures for respiratory pathogens in 2 years prior to screening will be summarized for the FAS. Further, the CFTR genotype for each subject will be provided in an individual subject data listing.

8.2.3 Prior and Concomitant Medications

Medications will be coded using the World Health Organization Drug Dictionary Enhanced (WHODDE) and categorized as follows:

For Parts 1 and 3:

Prior medication: any medication that started before the first dose date of study drug, regardless of when the medication ended.

Concomitant medication: medication continued or newly received on or after the first dose date of study drug through the end of the TE period.

Post-treatment medication: medication continued or newly received after the TE period.

For Part 2:

Prior medication: any medication that started before the first dose date of study drug in the Run-in Period, regardless of when the medication ended.

Concomitant medication during the Run-in Period: medication continued or newly received on or after the first dose date of study drug during the Run-in Period through the end of the TE period for the Run-in Period.

Concomitant medication during the Treatment Period: medication continued or newly received on or after the first dose date of study drug during the Treatment Period through the end of the TE period for the Treatment Period.

Post-treatment medication: medication continued or newly received after the TE period.

A given medication may be classified as follows: prior, concomitant, post-treatment, both prior and concomitant, both concomitant and post-treatment, or prior, concomitant, and

post-treatment. In Part 2, concomitant may be concomitant during the Run-in Period, or concomitant during the Treatment Period, or both.

If a medication has a completely missing or partially missing start/stop date and it cannot be determined whether it was taken before the first dose date of study drug, concomitantly, or after the TE period, it will be classified as prior, concomitant, and post-treatment.

Prior medications and concomitant medications will be summarized descriptively using frequency tables by preferred name.

Summaries of medications will be based on the FAS, and presented by treatment group and overall for each part.

Post-treatment medications will be listed by subject.

Details for imputing missing or partial start and/or stop dates of medication are described in Appendix C.

8.2.4 Study Drug Exposure

Study drug exposure (in days) will be calculated as: last dose date of study drug – first dose date of study drug + 1 day, regardless of study drug interruption, and will be summarized descriptively. Study drug exposure will be summarized for the overall study drug period, which includes the Treatment Period for Parts 1 and 3, and the Run-in Period and the Treatment Period for Part 2. Further, study drug exposure for the Treatment Period in Part 2 will also be summarized descriptively.

Study drug exposure (in weeks) will be summarized descriptively by the number of subjects (n), mean, SD, SE, median, min, and max. It will also be summarized in categories for Treatment Period: ≤ 2 weeks, $>2 - \leq 4$ weeks, and > 4 weeks (for Parts 1 and 3); and ≤ 2 weeks, $>2 - \leq 4$ weeks, $>4 - \leq 8$ weeks, >8 weeks (for Part 2), using counts and percentages. Additionally, the total study drug exposure, defined as the sum total of the study drug exposure across all subjects (in patient-weeks), will be provided.

Exposure summaries will be based on the Safety Set, and presented by treatment group and overall, for each part. For Part 2, exposure summaries will be based on the Safety Set for the Treatment Period.

8.2.5 Study Drug Compliance

Percentage of tablets taken will be calculated as: $100 \times [(\text{total number of tablets dispensed}) - (\text{total number of tablets returned})] / (\text{total number of tablets planned to be taken per day} \times \text{duration of study drug exposure in days})$. The maximum percentage of tablets taken will be 100%.

Study drug compliance will be calculated as: $100 \times [1 - (\text{total number of days of study drug interruption}) / (\text{duration of study drug exposure in days})]$. A study drug interruption on a given day will be determined by an interruption of all drugs on that day.

Percentage of tablets taken and study drug compliance will be summarized descriptively by the number of subjects (n), mean, SD, SE, median, min, and max. It will also be summarized in categories: $<80\%$ and $\geq 80\%$ using frequency tables.

For all parts, study drug compliance and percentage of tablets taken will be summarized for Period 1 in the Treatment Period only.

Percentage of tablets taken and study drug compliance summaries will be based on the FAS, and presented by treatment group and overall, for each part.

8.2.6 Important Protocol Deviations

An important protocol deviation (IPD) is a deviation that may significantly affect the completeness, accuracy, or reliability of the study data or that may significantly affect a subject's rights, safety, or well-being. IPD rules will be developed and finalized before database lock.

The protocol deviations that should be considered as potential IPDs include, but are not limited to:

- Subject was enrolled in the study despite the violation of inclusion/exclusion criteria
- Subject was less than 80% compliant with study drug
- Subject received prohibited concomitant medications
- Subject received the wrong treatment or incorrect doses
- Subject remained in the study despite meeting withdrawal criteria

Occurrence of any of these events should be considered as potential IPDs, but a blinded team should categorize them as IPDs only if they have the potential to significantly affect the completeness, accuracy, or reliability of the study data or that may significantly affect a subject's rights, safety, or well-being.

IPDs will be provided in an individual subject data listing for each part. Details of the IPD rules are provided in Appendix D.

8.3 Efficacy Analysis

All efficacy analyses described in this section will be based on the FAS, unless otherwise specified.

The analysis will include all available measurements through the last scheduled Treatment Period visit including measurements after treatment discontinuation, per the visit windowing rules described in Appendix B.

Except the sensitivity analyses, the post-dose measurements on the same day (e.g. days when spirometry is repeated pre- and post-dose) will not be used for any model-based analyses, but only reported in descriptive safety analyses.

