3 SCHEDULE OF ASSESSMENTS

Schedules of Assessments are provided in [Table 3-1](#) for Part 1, [Table 3-2](#) for Part 2, and [Table 3-3](#) for Part 3. All visits will be scheduled relative to the Day 1 Visit (first dose of VX-659 or VX-659 matched placebo).

Informed consent must be completed before any assessments are done at the Screening Visit. The Cystic Fibrosis Questionnaire-Revised (CFQ-R) assessment must be completed before any other assessment at the clinic visits when it is required. Other assessments may be performed in any order when more than 1 assessment is required at a particular time point. All assessments will be performed before dosing, unless noted otherwise.

Table 3-1 Study VX16-659-101 Part 1 (Subjects with F/MF genotypes): Schedule of Assessments

Event/Assessment ^a	Screening Period		Treatment Period (5 weeks)				ETT Visit ^b	Safety Follow-up 28 (± 7) Days After Last Dose
			Period 1 ^c (4 weeks)			Period 2		
	Screening Visit Days -28 to -1	Stratification Visit ^d Day -27 to -1	Day 1	Day 15 (± 2 days)	Day 29 (± 2 days)	Day 33 Visit ^e		
Informed consent	X							
Randomization ^f			X					
Study drug dosing ^g			Day 1 through Day 33 Visit					
Demographics	X							
Medical history	X							
CFTR genotype ^h	X							
Height ⁱ	X							
Weight ⁱ	X		X	X	X		X	

- ^a All assessments will be performed predose, unless noted otherwise. Assessments that are collected predose and postdose will only be collected once if study drug is not administered on the day of the visit (i.e., if subject prematurely discontinued study drug treatment).
- ^b If the subject prematurely discontinues study drug treatment, an Early Termination of Treatment (ETT) Visit should be scheduled as soon as possible after the decision to discontinue study drug treatment. Subjects who prematurely discontinue treatment will be required to complete the Safety Follow-up Visit. If the ETT Visit occurs 3 or more weeks after the last dose of study drug, the ETT Visit will replace the Safety Follow-up Visit (a separate Safety Follow-up Visit is not required).
- ^c To be eligible to continue into the Treatment Period, subjects must have stable CF disease and have remained on stable CF medication regimen during the 28 days before the Day 1 Visit AND must not have had an acute non-CF illness within 14 days before the Day 1 Visit. See Section 9.1.4.

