- ^d The spirometry assessment used for stratification must be performed at least 14 days after the last dose of any previous CFTR modulator treatment. Therefore, subjects being treated with 1 or more CFTR modulators (investigational or approved) within 14 days of the Screening Visit must have a separate Stratification Visit at least 14 days after the subject’s last CFTR modulator dose. For subjects not being treated with any CFTR modulators within 14 days of the Screening Visit, the Screening Visit spirometry assessment can be used for stratification.
- ^e The Day 33 Visit may occur 3 to 6 days after the actual date of the Day 29 Visit.
- ^f Randomization may occur on the previous day (Day -1) after all inclusion and exclusion criteria and criteria for entry into the Treatment Period (see footnote c) have been confirmed.
- ^g On days of scheduled visits, the in-clinic dose of study drugs will be given in the morning, at least 6 hours apart from any other scheduled dose and after all predose assessments are complete. The last dose of VX-659 in Part 1 Period 1 will be the morning dose on the Day 29 Visit. The last dose of TEZ/IVA in Part 1 Period 2 will be the morning dose on the Day 33 Visit. Refer to Section 9.7 for details.
- ^h CFTR genotyping will be performed for all subjects. If the screening CFTR genotype result is not received before randomization, a previous CFTR genotype laboratory report may be used to establish eligibility (see inclusion criterion 6).
- ⁱ Weight and height will be measured with shoes off.

Table 3-1 Study VX16-659-101 Part 1 (Subjects with F/MF genotypes): Schedule of Assessments

Event/Assessment ^a	Screening Period		Treatment Period (5 weeks)				ETT Visit ^b	Safety Follow-up 28 (± 7) Days After Last Dose
			Period 1 ^c (4 weeks)		Period 2			
	Screening Visit Days -28 to -1	Stratification Visit ^d Day -27 to -1	Day 1	Day 15 (± 2 days)	Day 29 (± 2 days)	Day 33 Visit ^e		
Physical examination ^j	Complete		Abbrev.	Abbrev.	Abbrev.		Abbrev.	Complete
Vital signs ^k	X		X	X	X	X	X	X
Pulse oximetry ^k	X		X	X	X	X	X	X
Standard 12-lead ECG ^l	X		X	X	X		X	X
Sweat chloride ^{m,p}	X		X	X	X	X	X	X
Spirometry ⁿ	X	X	X	X	X	X	X	X
CFQ-R ^{o,p}			X	X	X			
Urinalysis ^p	X		X	X	X		X	X
Pregnancy test (females of childbearing potential)	Serum		Urine		Urine		Serum	Serum
FSH ^q	X							

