7.2 Secondary Endpoints

- Absolute change in sweat chloride concentrations from baseline through the Day 29 Visit
- Relative change in ppFEV₁ from baseline through the Day 29 Visit
- Absolute change in Cystic Fibrosis Questionnaire-Revised (CFQ-R) respiratory domain score from baseline at the Day 29 Visit
- PK parameters of VX-659, TEZ, M1-TEZ, IVA, M1-IVA, and VX-561

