9.1.6 Early Termination of Treatment

If a subject prematurely discontinues treatment at any time after enrollment, an Early Termination of Treatment (ETT) Visit should be scheduled as soon as possible after the decision to terminate study drug treatment. Subjects who prematurely discontinue treatment will also be required to complete the Safety Follow-up Visit, approximately 28 days after their last dose of study drug.

If the ETT Visit occurs 3 weeks or later following the last dose of study drug, then the ETT Visit will replace the Safety Follow-up Visit, and a separate Safety Follow-up Visit will not be required.

If a subject withdraws from the study and also withdraws consent for disclosure of future information, no further evaluations should be performed and no additional data should be collected. Vertex may retain and continue to use any data collected before such withdrawal of consent.

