9.10 Removal of Subjects

Subjects may withdraw from the study at any time at their own request. Subjects may be withdrawn from study drug treatment at any time at the discretion of the investigator or Vertex for safety reasons, behavior, noncompliance with study drug dosing or study procedures, ineligibility, or administrative reasons.

Whenever possible, subjects who have been withdrawn from study drug treatment will continue on study, however, Vertex retains the right to remove a subject from the study.

Subjects who have been randomized and whose screening *CFTR* genotype does not confirm study eligibility must be discontinued from the study, even if a previous *CFTR* genotype laboratory report was used to establish eligibility.

If a subject does not return for a scheduled visit, reasonable effort will be made to contact the subject. In any circumstance, reasonable effort will be made to document subject outcome. The investigator will inquire about the reason for withdrawal, request that the subject return all unused investigational product(s), request that the subject return for a Safety Follow-up Visit, if applicable (see Section 9.1.6), and follow up with the subject regarding any unresolved AEs.

If the subject withdraws consent for the study, no further evaluations will be performed and no additional data will be collected. Vertex may retain and continue to use the study data and samples collected. The study data and the samples may be used for the development of the study compound, other drugs, or diagnostics, in publications and presentations, or for education purposes. If the subject withdraws from the study, the study data and samples collected will remain part of the study. A subject will not be able to request the withdrawal of his/her information from the study data. A subject may request destruction of the samples collected from him/her during the study as long as those samples can be identified as his/her samples. Any information that already has been obtained from the samples will continue to be used.

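### CFQ-R is not scheduled at the Early Termination visit in any part, so a subject who stops drug before Day 15 and attends no further scheduled visits leaves the CFQ-R model but stays in the ppFEV1 and sweat chloride models

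*SAP*

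**What the plan says.** The endpoint (Protocol 7.2, SAP 5.1.2) is "Absolute change in Cystic Fibrosis Questionnaire-Revised (CFQ-R) respiratory domain score from baseline at the Day 29 Visit". SAP 8.3.2.2 analyses it with an MMRM similar to that for ppFEV1. The ppFEV1 model (SAP 8.3.1.1) assumes missing data are missing at random and imputes nothing.

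On data after stopping, SAP 8.3 uses whatever measurements are available up to the final Treatment Period visit, "including measurements after treatment discontinuation, per the visit windowing rules" of Appendix B.

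On visits after stopping, Protocol 9.1.6 says "an Early Termination of Treatment (ETT) Visit should be scheduled as soon as possible after the decision to terminate study drug treatment", and it also requires the Safety Follow-up Visit. It names no other visit. Protocol 9.10 adds: "Whenever possible, subjects who have been withdrawn from study drug treatment will continue on study". Footnote a of each schedule allows for visits without dosing: assessments normally taken before and after the dose "will only be collected once if study drug is not administered on the day of the visit", with premature discontinuation given as the reason.

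Protocol Tables 3-1 to 3-3 and SAP Tables 11-1 to 11-3 mark spirometry and sweat chloride at the ETT Visit in every part. The CFQ-R row is blank at the ETT Visit and at Safety Follow-up in every part.

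**The concern.** Three efficacy measures are analysed with similar models and the same rule on post-discontinuation data. At the one visit designed for subjects who stop early, two of the three are collected and the third is not. The documents give no reason for the difference.

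CFQ-R respiratory is the only patient-reported measure among the named primary and secondary endpoints. If some subjects stop because they feel unwell, their symptom scores are the ones most likely to be absent, and missing at random is then hardest to defend. The CFQ-R result could rest on fewer subjects than the ppFEV1 result beside it. Arms are small: 18 or 9 subjects in Parts 1 and 2, and about 18 and 6 in Part 3 (24 subjects at 3:1). Protocol 9.11 offers replacement during treatment only for non-safety withdrawals, so subjects withdrawn for safety reasons would not be replaced.

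**Working it through.** **1. Schedules** (Protocol Tables 3-1 to 3-3, repeated in SAP Tables 11-1 to 11-3)

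| Part | CFQ-R marked at | CFQ-R at ETT | Sweat chloride at ETT | Spirometry at ETT |
|---|---|---|---|---|
| 1 | Days 1, 15, 29 | no | yes | yes |
| 2 | Days 1, 15, 29, 43, 57 | no | yes | yes |
| 3 | Days 1, 15, 29 | no | yes | yes |

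CFQ-R is collected at the ETT Visit in 0 of 3 parts, against 3 of 3 for each of the others. It is collected at Safety Follow-up in 0 of 3.

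**2. What each kind of early stopper contributes**

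- *Stops before Day 15, attends only ETT and Safety Follow-up.* Spirometry and sweat chloride from an ETT Visit on or before Day 22 fall in the Day 15 window [1, 22] and enter those models. There is no post-baseline CFQ-R, so the subject contributes nothing to the CFQ-R model.
- *Stops between Days 15 and 29, attends only ETT and Safety Follow-up.* Day 15 CFQ-R is in the model; Day 29 is missing.
- *Stops in Period 1 but keeps attending.* CFQ-R is taken at the remaining visits and nothing is lost.
- *Stops in Period 2 (Parts 1 and 2).* The Day 29 visit has already passed.

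**3. Where an ETT score would go.** Under the CFQ-R windows in Appendix B, a score on or before Day 22 maps to Day 15. A later score maps to Day 29 if it falls in (22, 45] in Part 1, (22, 36] in Part 2 or (22, 43] in Part 3. If a Day 15 visit score already exists, an ETT score in the same window adds nothing, because Appendix B gives the scheduled visit priority for efficacy measures.

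**4. Share of an arm.** One subject is 1/18 = 5.6%, 1/9 = 11.1% or 1/6 = 16.7%. The documents give no early-stop rate. Assumed rates of 5% to 15% give 0.9 to 2.7 subjects in an arm of 18 and about 0.5 to 1.4 in an arm of 9.

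**5. Illustrative shift.** The documents give no SD, effect size or power for CFQ-R, so there is no planned figure to reproduce. Assume one subject with a change of -15 and a mean of +10 in the others. Omitting that subject raises the raw arm mean by (mean of others - subject's value)/n:

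- n=18: (10 - (-15))/18 = 25/18 = 1.4 points
- n=9: 25/9 = 2.8 points
- n=6: 25/6 = 4.2 points

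These treat the ETT score as a Day 29 value. If it falls on or before Day 22, it reaches the Day 29 estimate only through the within-subject correlation. Ignoring covariates and with the other subjects complete, the Day 29 mean moves by slope × 25/n, where the slope is that of Day 29 on Day 15. The documents give no slope. For assumed values of 0.5 to 0.8:

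- n=18: 0.5 × 1.39 = 0.7 to 0.8 × 1.39 = 1.1 points
- n=9: 0.5 × 2.78 = 1.4 to 0.8 × 2.78 = 2.2 points

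The shift is zero if nobody stops early.

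**The case against.** The strongest reply is that the plan already provides for off-treatment data. Section 9.10 keeps subjects on study where possible, and footnote a foresees visits without dosing, so CFQ-R can be completed at Days 15 and 29 after a stop. This stands. A reader might infer from the blank ETT cells that CFQ-R is lost in everyone who stops early; the four cases above show that it is not. What remains is that 9.1.6 and 9.10 do not firmly require those visits.

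A reader might also infer that the SAP contradicts the schedule. It does not: the rule covers available measurements, and a questionnaire never scheduled at a visit is not one of them.

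A third reply is that an ETT score would not supply Day 29 for a subject who stops before Day 15 and is seen promptly. This is right. Such a score would still keep the subject in the model, inform Day 29 indirectly and make missing at random more plausible.

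The omission may also be deliberate. Spirometry is a safety endpoint in the SAP as well, and Appendix B notes for Part 3 that Safety Follow-up has no CFQ-R. The first point gives spirometry its own reason to be at the ETT Visit, but not sweat chloride.

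Finally, one might assume that the loss flatters the active arms. The documents give neither reasons nor rates for stopping. Losing a poorly performing subject from placebo or TEZ/IVA would shrink the between-group difference.

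**Conclusion.** This is a real but narrow data-collection gap in a secondary endpoint. It affects subjects who stop in Period 1 and do not attend the remaining scheduled visits. Those who stop before Day 15 leave the CFQ-R model while staying in the ppFEV1 and sweat chloride models, provided an ETT value is obtained in time for the windows.

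The size of any bias cannot be computed from the documents. The point shifts above show scale only: they rest on assumed scores and an assumed slope, and the raw-mean figures overstate the effect on the Day 29 estimate when the ETT Visit is on or before Day 22. The direction of any effect on the between-group difference depends on which arm loses subjects. No stated sample size, power or alpha changes. The change is worth making because it costs little and the arms are small.

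**What to change.** 1. Mark CFQ-R at the ETT Visit in Protocol Tables 3-1 to 3-3 and SAP Tables 11-1 to 11-3, completed before any other assessment, as at other visits.
2. Let the score enter the CFQ-R windows already in Appendix B. No new window is needed.
3. Reconcile Protocol 9.1.6 with 9.10: state whether subjects who stop drug are expected at the remaining scheduled assessments through Day 29. Those visits supply the Day 29 score directly, which an early ETT Visit cannot.

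The cost is a few minutes for each early stopper, one added cell in each of six tables, a clarifying sentence on attendance and possibly a small eCRF change.
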